10.1.2 Informed Consent Process

- The Investigator or his/her representative will explain the nature of the study to the participant and answer all questions regarding the study.
- Participants must be informed that their participation is voluntary. Participants will be required to sign a statement of informed consent that meets the requirements of 21 CFR 50, local regulations, ICH guidelines, Health Insurance Portability and

Accountability Act (HIPAA) requirements, where applicable, and the IRB/IEC or study center.

- The medical record must include a statement that written informed consent was obtained before the participant was enrolled in the study and the date the written consent was obtained. The authorized person obtaining the informed consent must also sign the ICF.
- Participants must be re-consented to the most current version of the ICF(s) during their participation in the study.
- A copy of the ICF(s) must be provided to the participant.

A participant who is rescreened is not required to sign another ICF if the rescreening occurs within the screening window (ie within 1 week of the previous screening).

10.1.3 Data Protection

- Participants will be assigned a unique identifier by the Sponsor. Any participant records or datasets that are transferred to the Sponsor will contain the identifier only; participant names or any information which would make the participant identifiable will not be transferred.
- The participant must be informed that his/her personal study-related data will be used by the Sponsor in accordance with local data protection law. The level of disclosure must also be explained to the participant.
- The participant must be informed that his/her medical records may be examined by Clinical Quality Assurance auditors or other authorized personnel appointed by the Sponsor, by appropriate IRB/IEC members, and by inspectors from regulatory authorities.
- Participants' race and ethnicity (race: Asian, Black or African American, White, Other not reported, Unknown; ethnicity: Hispanic, Not Hispanic) will be collected in this study because these data are required by several regulatory authorities (eg, on African American population for US FDA).
- The data collected in this study will only be used for the purpose(s) of the study and to document the evaluation of the benefit/risk ratio, efficacy, and safety of the product(s). They may be further processed if they have been anonymized.

10.1.4 Committees Structure

10.1.4.1 Steering Committee

The Steering Committee is responsible for providing study oversight. In this capacity, the Steering Committee shall address and resolve scientific issues encountered during the study. The Steering Committee is also responsible for ensuring accurate reporting of the study results.

10.1.4.2 Data Monitoring Committee

An independent DMC with members who are independent from the Sponsor and the Investigators will meet on a regular basis and will be responsible for:

- Review of accumulating clinical study safety data, and
- Making a recommendation to the Sponsor regarding the study following each meeting

The DMC reviews and analyzes, on a regular basis, unblinded safety data throughout the study, as well as safety data from the other ongoing clinical studies conducted with efpeglenatide (a single DMC for the whole efpeglenatide program). Details describing the DMC processes and procedures are outlined in the DMC Charter. To maintain continuous blinding and study integrity, the analysis will be conducted by an independent statistician who will directly transfer data to DMC members, and measures will be taken to ensure the validity of the data.

10.1.4.3 Clinical Endpoint Committee

An independent CEC will be composed of experts in the field of cardiology, neurology, and gastroenterology (and other appropriate medical specialties as needed). This committee will be independent from the Sponsor and the Investigators, and will be implemented to review, assess and/or adjudicate all events of death, selected CV events (non-fatal MI, stroke, unstable angina leading to hospitalization, and heart failure leading to hospitalization), pancreatic events and other selected AEs (to be defined in the CEC charter). This review will be conducted in a blinded manner with regard to study treatment.

10.1.4.4 Independent Expert

An independent ophthalmologist expert will review in a treatment-blinded manner all reported AEs suspected to be diabetic retinopathy to assess the presence of retinopathy and the relationship of reported AE to IMP.

Investigators are reminded that all patients should have eye examinations based on their retinopathy status, performed by a professional eye care provider according to International Council of Ophthalmology (ICO) guidelines (19) or local standards. Especially for patients at high risk, this should occur at minimum quarterly.

10.1.5 Dissemination of Clinical Study Data

Sanofi shares information about clinical trials and results on publically accessible websites, based on company commitments, international and local legal and regulatory requirements, and other clinical trial disclosure commitments established by pharmaceutical industry associations. These websites include clinicaltrials.gov, European Union clinicaltrialregister (eu.ctr), and sanofi.com, as well as some national registries.

In addition, results from clinical trials in patients are required to be submitted to peer-reviewed journals following internal company review for accuracy, fair balance and intellectual property. For those journals that request sharing of the analyzable data sets that are reported in the

publication, interested researchers are directed to submit their request to clinicalstudydatarequest.com.

Individual participant data and supporting clinical documents are available for request at clinicalstudydatarequest.com. While making information available we continue to protect the privacy of participants in our clinical trials. Details on data sharing criteria and process for requesting access can be found at this web address: clinicalstudydatarequest.com.

10.1.6 Data Quality Assurance

- All participant data relating to the study will be recorded on printed or electronic CRF unless transmitted to the Sponsor or designee electronically (eg, laboratory data). The Investigator is responsible for verifying that data entries are accurate and correct by physically or electronically signing the CRF.
- The Investigator must maintain accurate documentation (source data) that supports the information entered in the CRF.
- The Investigator must permit study-related monitoring, audits, IRB/IEC review, and regulatory agency inspections and provide direct access to source data documents.
- The Sponsor or designee is responsible for the data management of this study including quality checking of the data.
- Study monitors will perform ongoing source data verification to confirm that data entered into the CRF by authorized site personnel are accurate, complete, and verifiable from source documents; that the safety and rights of participants are being protected; and that the study is being conducted in accordance with the currently approved protocol and any other study agreements, ICH GCP, and all applicable regulatory requirements.
- Records and documents, including signed ICFs, pertaining to the conduct of this study must be retained by the Investigator for 15 years after study completion unless local regulations or institutional policies require a longer retention period. No records may be destroyed during the retention period without the written approval of the Sponsor. No records may be transferred to another location or party without written notification to the Sponsor.

10.1.7 Source documents

- Source documents provide evidence for the existence of the participant and substantiate the integrity of the data collected. Source documents are filed at the Investigator's site.
- Data reported on the CRF or entered in the eCRF that are transcribed from source documents must be consistent with the source documents or the discrepancies must be explained. The Investigator may need to request previous medical records or transfer records, depending on the study. Also, current medical records must be available.
- Definition of what constitutes source data can be found in a separate study document.

10.1.8 Study and Site Closure

The Sponsor designee reserves the right to close the study site or terminate the study at any time for any reason at the sole discretion of the Sponsor. Study sites will be closed upon study completion. A study site is considered closed when all required documents and study supplies have been collected and a study-site closure visit has been performed.

The Investigator may initiate study-site closure at any time, provided there is reasonable cause and sufficient notice is given in advance of the intended termination.

Reasons for the early closure of a study site by the Sponsor or Investigator may include but are not limited to:

- Failure of the Investigator to comply with the protocol, the requirements of the IRB/IEC or local health authorities, the Sponsor's procedures, or GCP guidelines
- Inadequate recruitment of participants by the Investigator
- Discontinuation of further study intervention development

10.1.9 Publication Policy

- The results of this study may be published or presented at scientific meetings. If this is foreseen, the Investigator agrees to submit all manuscripts or abstracts to the Sponsor before submission. This allows the Sponsor to protect proprietary information and to provide comments.
- The Sponsor will comply with the requirements for publication of study results. In accordance with standard editorial and ethical practice, the Sponsor will generally support publication of multicenter studies only in their entirety and not as individual site data. In this case, a coordinating Investigator will be designated by mutual agreement.
- Authorship will be determined by mutual agreement and in line with International Committee of Medical Journal Editors authorship requirements.

10.2 APPENDIX 2: CLINICAL LABORATORY TESTS

The tests detailed in [Table 9](#) will be performed by the central laboratory.

- Local laboratory results are only required in the event that the central laboratory results are not available in time for either study intervention administration and/or response evaluation. If a local sample is required, it is important that the sample for central analysis is obtained at the same time. Additionally, if the local laboratory results are used to make either a study intervention decision or response evaluation, the results must be entered into the CRF.
- Protocol-specific requirements for inclusion or exclusion of participants are detailed in [Section 5](#) of the protocol.
- Additional tests may be performed at any time during the study as determined necessary by the Investigator or required by local regulations.

Table 9 - Protocol-required safety laboratory assessments

Laboratory assessments	Parameters			
Hematology	Platelet count		RBC indices:	White blood cell (WBC) count with differential:
	Red blood cell (RBC) count		Mean Corpuscular Volume (MCV)	Neutrophils
	White blood cell (WBC) count		Mean Corpuscular Hemoglobin (MCH)	Lymphocytes
	Hemoglobin		%Reticulocytes	Monocytes
	Hematocrit			Eosinophils Basophils
Clinical chemistry ^a	Uric acid	Potassium	Aspartate aminotransferase (AST)	Total bilirubin ^b
	Glucose (non-fasting)	Sodium	Alanine aminotransferase (ALT)	Creatinine
	Amylase	Calcitonin	Alkaline phosphatase	Estimated creatinine clearance
	Lipase			
Lipid profile	Triglyceride(non-fasting)		Cholesterol: Total cholesterol Low-density lipoprotein cholesterol High-density lipoprotein cholesterol	
Anti-drug antibodies	
 • Treatment boosted and treatment induced ADA • ADAs cross-reacting to endogenous glucagon • ADAs directed against the PEG linker of epeglenatide 			
Routine urinalysis	
 • Specific gravity • pH, glucose, protein, blood, ketones, leukocyte • Microscopic examination (if blood or protein is abnormal) 			
Other urinalysis	
 • Urinary albumin-to-creatinine ratio by spot urine 			
Other screening tests	
 • Follicle-stimulating hormone and estradiol (as needed in women of non-childbearing potential only) • Serum human chorionic gonadotropin (HCG) pregnancy test (as needed for women of childbearing potential)^c • Serology (hepatitis B surface antigen [HBsAg], and hepatitis C virus antibody) 			
The results of each test will be transferred from Central Laboratory in the Clinical Database				

NOTES :

- ^a Details of liver chemistry stopping criteria and required actions and follow-up assessments after liver stopping or monitoring event are given in Appendix 5 (Section 10.5). All events of ALT $\geq 3 \times$ upper limit of normal (ULN) and bilirubin $\geq 2 \times$ ULN (>35% direct bilirubin) or ALT $\geq 3 \times$ ULN and international normalized ratio (INR) >1.5, if INR measured which may indicate severe liver injury (possible Hy's Law) must be reported as an SAE (excluding studies of hepatic impairment or cirrhosis).
- ^b In case of values above the normal range, differentiation in conjugated and non-conjugated bilirubin
- ^c Urine pregnancy testing will be performed subsequent to Screening. If the urine test is positive, serum β -HCG should be tested for confirmation of the pregnancy

Investigators must document their review of each laboratory safety report.

10.3 APPENDIX 3: ADVERSE EVENTS: DEFINITIONS AND PROCEDURES FOR RECORDING, EVALUATING, FOLLOW-UP, AND REPORTING

DEFINITION OF AE

AE definition

- An AE is any untoward medical occurrence in a patient or clinical study participant, temporally associated with the use of study intervention, whether or not considered related to the study intervention.
- NOTE: An AE can therefore be any unfavorable and unintended sign (including an abnormal laboratory finding), symptom, or disease (new or exacerbated) temporally associated with the use of study intervention.

Events meeting the AE definition

- Any abnormal laboratory test results (hematology, clinical chemistry, or urinalysis) or other safety assessments (eg, ECG, radiological scans, vital signs measurements), including those that worsen from baseline, considered clinically significant in the medical and scientific judgment of the Investigator (ie, not related to progression of underlying disease).
- Exacerbation of a chronic or intermittent pre-existing condition including either an increase in frequency and/or intensity of the condition.
- New conditions detected or diagnosed after study intervention administration even though it may have been present before the start of the study.
- Signs, symptoms, or the clinical sequelae of a suspected drug-drug interaction.
- Signs, symptoms, or the clinical sequelae of a suspected overdose of either study intervention or a concomitant medication.
- “Lack of efficacy” or “failure of expected pharmacological action” per se will not be reported as an AE or SAE. However, the signs, symptoms, and/or clinical sequelae resulting from lack of efficacy will be reported as AE or SAE if they fulfil the definition of an AE or SAE.

Events NOT meeting the AE definition

- Any clinically significant abnormal laboratory findings or other abnormal safety assessments which are associated with the underlying disease, unless judged by the Investigator to be more severe than expected for the participant’s condition.
- The disease/disorder being studied or expected progression, signs, or symptoms of the disease/disorder being studied, unless more severe than expected for the participant’s condition.

- Medical or surgical procedure (eg, endoscopy, appendectomy): the condition that leads to the procedure is the AE.
- Situations in which an untoward medical occurrence did not occur (social and/or convenience admission to a hospital).
- Anticipated day-to-day fluctuations of pre-existing disease(s) or condition(s) present or detected at the start of the study that do not worsen

DEFINITION OF SAE

If an event is not an AE per definition above, then it cannot be an SAE even if serious conditions are met (eg, hospitalization for signs/symptoms of the disease under study, death due to progression of disease).

A SAE is defined as any untoward medical occurrence that, at any dose:

a) Results in death

b) Is life-threatening

The term 'life-threatening' in the definition of 'serious' refers to an event in which the participant was at risk of death at the time of the event. It does not refer to an event, which hypothetically might have caused death, if it were more severe.

c) Requires inpatient hospitalization or prolongation of existing hospitalization

In general, hospitalization signifies that the participant has been detained (usually involving at least an overnight stay) at the hospital or emergency ward for observation and/or treatment that would not have been appropriate in the physician's office or outpatient setting. Complications that occur during hospitalization are AEs. If a complication prolongs hospitalization or fulfills any other serious criteria, the event is serious. When in doubt as to whether "hospitalization" occurred or was necessary, the AE should be considered serious.

Hospitalization for elective treatment of a pre-existing condition that did not worsen from baseline is not considered an AE.

d) Results in persistent disability/incapacity

- The term disability means a substantial disruption of a person's ability to conduct normal life functions.
- This definition is not intended to include experiences of relatively minor medical significance such as uncomplicated headache, nausea, vomiting, diarrhea, influenza, and accidental trauma (eg, sprained ankle) which may interfere with or prevent everyday life functions but do not constitute a substantial disruption.

e) Is a congenital anomaly/birth defect

f) Other situations:

- Medical or scientific judgment should be exercised in deciding whether SAE reporting is appropriate in other situations such as important medical events that may not be immediately life-threatening or result in death or hospitalization but may jeopardize

the participant or may require medical or surgical intervention to prevent one of the other outcomes listed in the above definition. These events should usually be considered serious.

Examples of such events include invasive or malignant cancers, intensive treatment in an emergency room or at home for allergic bronchospasm, blood dyscrasias or convulsions that do not result in hospitalization, or development of drug dependency or drug abuse.

RECORDING AND FOLLOW-UP OF AE AND/OR SAE

AE and SAE recording

- When an AE/SAE occurs, it is the responsibility of the Investigator to review all documentation (eg, hospital progress notes, laboratory reports, and diagnostics reports) related to the event.
- The Investigator will then record all relevant AE/SAE information in the CRF.
- It is **not** acceptable for the Investigator to send photocopies of the participant's medical records to the Sponsor's representative in lieu of completion of the AE/SAE CRF page.
- There may be instances when copies of medical records for certain cases are requested by the Sponsor's representative. In this case, all participant identifiers, with the exception of the participant number, will be redacted on the copies of the medical records before submission to the Sponsor's representative.
- The Investigator will attempt to establish a diagnosis of the event based on signs, symptoms, and/or other clinical information. Whenever possible, the diagnosis (not the individual signs/symptoms) will be documented as the AE/SAE.

Assessment of intensity

The Investigator will make an assessment of intensity for each AE and SAE reported during the study and assign it to 1 of the following categories:

- **Mild:** An event that is easily tolerated by the participant, causing minimal discomfort and not interfering with everyday activities.
- **Moderate:** An event that causes sufficient discomfort and interferes with normal everyday activities.
- **Severe:** An event that prevents normal everyday activities. An AE that is assessed as severe should not be confused with a SAE. Severe is a category utilized for rating the intensity of an event; and both AEs and SAEs can be assessed as severe.

An event is defined as 'serious' when it meets at least 1 of the predefined outcomes as described in the definition of an SAE, NOT when it is rated as severe.

Assessment of causality

- The Investigator is obligated to assess the relationship between study intervention and each occurrence of each AE/SAE.

- A "reasonable possibility" of a relationship conveys that there are facts, evidence, and/or arguments to suggest a causal relationship, rather than a relationship cannot be ruled out.
- The Investigator will use clinical judgment to determine the relationship.
- Alternative causes, such as underlying disease(s), concomitant therapy, and other risk factors, as well as the temporal relationship of the event to study intervention administration will be considered and investigated.
- The Investigator will also consult the IB and/or Product Information, for marketed products, in his/her assessment.
- For each AE/SAE, the Investigator **must** document in the medical notes that he/she has reviewed the AE/SAE and has provided an assessment of causality.
- There may be situations in which an SAE has occurred and the Investigator has minimal information to include in the initial report to the Sponsor's representative. However, **it is very important that the Investigator always make an assessment of causality for every event before the initial transmission of the SAE data to the Sponsor's representative.**
- The Investigator may change his/her opinion of causality in light of follow-up information and send a SAE follow-up report with the updated causality assessment.
- The causality assessment is one of the criteria used when determining regulatory reporting requirements.

Follow-up of AEs and SAEs

- The Investigator is obligated to perform or arrange for the conduct of supplemental measurements and/or evaluations as medically indicated or as requested by the Sponsor's representative to elucidate the nature and/or causality of the AE or SAE as fully as possible. This may include additional laboratory tests or investigations, histopathological examinations, or consultation with other health care professionals.
- New or updated information will be recorded in the originally completed CRF.
- The Investigator will submit any updated SAE data to the the Sponsor's representative within 24 hours of receipt of the information.
- Please refer to [Section 8.3.3](#) for more details.

REPORTING OF SAES

SAE reporting to the Sponsor's representative via an electronic data collection tool

- The primary mechanism for reporting an SAE to the Sponsor's representative will be the electronic data collection tool.
- If the electronic system is unavailable for more than 24 hours, then the site will use the paper SAE data collection tool (see next section).
- The site will enter the SAE data into the electronic system as soon as it becomes available.

- After the study is completed at a given site, the electronic data collection tool will be taken off-line to prevent the entry of new data or changes to existing data.
- If a site receives a report of a new SAE from a study participant or receives updated data on a previously reported SAE after the electronic data collection tool has been taken off-line, then the site can report this information on a paper SAE form (see next section) or to the Sponsor's representative by telephone.
 - Contacts for SAE reporting can be found in a separate study document.

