8.3 ADVERSE EVENTS AND SERIOUS ADVERSE EVENTS

Adverse event of special interest

An AESI is an AE (serious or nonserious) of scientific and medical concern specific to the Sponsor's product or program, for which ongoing monitoring and immediate notification by the Investigator to the Sponsor is required. Such events may require further investigation in order to characterize and understand them. Adverse events of special interest may be added, modified or removed during a study by protocol amendment.

- Pregnancy of a female subject entered in a study as well as pregnancy occurring in a female partner of a male subject entered in a study with IMP (see [Section 8.3.5](#));
- Symptomatic overdose (serious or nonserious) with IMP
 - An overdose (accidental or intentional) with the IMP is an event suspected by the Investigator or spontaneously notified by the participant and defined as at least twice the planned dose (e.g. two or more injections) if given within 3 days (72 hours).
 - Of note, asymptomatic overdose has to be reported as a standard AE.
- ALT ≥ 3 ULN (if baseline ALT <ULN) Or ALT ≥ 2 times the baseline value (if baseline ALT \geq ULN) (Please refer to related flowchart in Appendix 5 [[Section 10.5](#)])

Adverse events requiring specific monitoring

An AE requiring specific monitoring is a serious or non-serious AE of scientific and medical concern specific to the Sponsor's product or program, for which ongoing monitoring may be appropriate. Such events may require further investigation to characterize and understand them. These events should be reported on the AE page and additional information required on specific e-CRF page (where applicable) and will only qualify for expedited reporting when serious (fulfilling SAE criteria).

The AE requiring specific monitoring for this study are:

- Severe GI events
- Severe hypoglycemia (see [Section 8.2.5](#))
- Pancreatic events (including abnormal values of pancreatic enzymes [see Appendix 6, [Section 10.6](#)])
- Calcitonin increase >5.9 pmol/L (20 pg/mL) and thyroid C-cell neoplasm (see Appendix 6, [[Section 10.6](#)])
- Acute renal failure (see Appendix 7 [[Section 10.7](#)])
- Diabetic retinopathy complications (will be reviewed by an independent ophthalmologist expert, see Appendix 1 [[Section 10.1.4.4](#)]); a written report from professional eye care provider will be required
- Severe injection site reactions
- Severe allergic reactions

- Severe immune complex disease

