8.3.1 Time period and frequency for collecting AE and SAE information

All SAEs and AEs will be collected from the signing of the ICF until the follow-up visit at the time points specified in the SoA ([Section 1.3](#)).

All SAEs and AESI will be recorded and reported to the Sponsor or designee within 24 hours, as indicated in Appendix 3 ([Section 10.3](#)). The Investigator will submit any updated SAE data to the Sponsor within 24 hours of it being available.

Investigators are not obligated to actively seek AE or SAE after conclusion of the study participation. However, if the Investigator learns of any SAE, including a death, at any time after a participant has been discharged from the study, and he/she considers the event to be reasonably related to the study intervention or study participation, the Investigator must promptly notify the Sponsor.

The method of recording, evaluating, and assessing causality of AE and SAE and the procedures for completing and transmitting SAE reports are provided in Appendix 3 ([Section 10.3](#)).

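### Appendix 3 triggers the paper SAE route only once an outage has outlasted the whole 24-hour reporting window of Section 8.3.1, so a site that waits for the trigger can report late

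*Protocol*

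**What the plan says.** Protocol Section 8.3.1 sets the limit: "All SAEs and AESI will be recorded and reported to the Sponsor or designee within 24 hours, as indicated in Appendix 3". It makes no exception for a system outage and does not say when the clock for the initial report starts. For AESIs, Section 8.3 sets a stricter tone: they are events "for which ongoing monitoring and immediate notification by the Investigator to the Sponsor is required".

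Appendix 3 (Section 10.3), under the reporting of SAEs, gives the procedure:

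- Normal route: "The primary mechanism for reporting an SAE to the Sponsor's representative will be the electronic data collection tool".
- During an outage: "If the electronic system is unavailable for more than 24 hours, then the site will use the paper SAE data collection tool".
- Next line, read in context as the step when the system returns: "The site will enter the SAE data into the electronic system as soon as it becomes available".
- After the tool has been taken off-line because the study is complete at a site: "then the site can report this information on a paper SAE form (see next section) or to the Sponsor's representative by telephone".

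For updated SAE data, Appendix 3 does define a clock start: "within 24 hours of receipt of the information".

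**The concern.** Section 8.3.1 sends the site to Appendix 3 to learn how to meet a 24-hour limit. The only in-study fallback stated there begins after a wait equal to that entire limit. The two clocks also measure different things: the limit concerns the report of an event, while the trigger counts how long the system has been down. A site that reads the outage sentence as its instruction, and waits, may find the reporting window closed when the fallback begins. In a shorter outage late in the window, the trigger is never reached at all.

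What is at stake is timely safety notification. Section 8.3.4 treats prompt SAE notification as essential to the sponsor's legal and ethical duties. The AESIs include ALT elevations, and Section 2.3 names potential liver toxicity as the exception to an otherwise class-typical safety profile. Section 8.3.7 also applies a 24-hour limit to endpoint events that the investigator considers related to the IMP. For AESIs the gap is slightly wider, because the outage sentence names SAEs only.

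**Working it through.** The plan gives no figure to reproduce here. The check sets the two rules side by side and works out the timing.

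**Inputs**

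- Reporting limit: 24 h (Section 8.3.1).
- Paper trigger: system unavailable for more than 24 h (Appendix 3).
- Clock start: site awareness, t = 0. This is an assumption. Section 8.3.1 gives no start for the initial report; Appendix 3 counts from receipt for updates, and Section 8.3.5 counts from learning of a pregnancy.
- s = hour at which the outage starts, relative to awareness (negative if it began before). D = length of the outage in hours.
- The site has not yet reported when the outage begins, and it waits for either the stated trigger or the return of the system.

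**Formulas**

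- If D > 24, paper opens just after t = s + 24.
- If D ≤ 24, the trigger is never met and the system returns at t = s + D.
- The report is late if the resulting time is beyond t = 24.

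**Results**

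| Outage start s | D > 24 h: paper opens just after | D ≤ 24 h: system returns at |
|---|---|---|
| −12 h | −12 + 24 = 12 h, in time | at most −12 + 24 = 12 h, in time |
| −1 h | −1 + 24 = 23 h, in time | at most −1 + 24 = 23 h, in time |
| 0 h | 0 + 24 = 24 h, late | at most 24 h, in time |
| 6 h | 6 + 24 = 30 h, late | 6 + D, late if D > 18 |
| 12 h | 12 + 24 = 36 h, late | 12 + D, late if D > 12 |
| 23 h | 23 + 24 = 47 h, late | 23 + D, late if D > 1 |

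Three cases follow.

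1. Outage begins before awareness (s < 0): s + 24 and s + D (with D ≤ 24) are both below 24, so the limit can always be met.
2. Outage begins at awareness (s = 0): late only if it lasts more than 24 h.
3. Outage begins after awareness and before the report is sent (s > 0): late whenever s + D > 24. For example, a 6 h outage starting at hour 23 ends at 23 + 6 = 29 h without the paper trigger ever being reached.

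So lateness needs three things together: the outage starts at or after awareness, it starts before the report is sent, and it is still running at hour 24.

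**The case against.** The strongest reply is that the passages do not contradict each other. Appendix 3 calls the electronic tool the primary mechanism, not the sole one. It makes paper mandatory after more than 24 hours of outage, but it does not forbid earlier paper or telephone reporting, and it does not suspend the 24-hour duty. A site that sends paper at hour 10 of an outage breaches neither section. This stands. A reader might infer that the two rules cannot both be obeyed, or that any site following Appendix 3 breaks the limit; the documents support neither. What remains is that the stated threshold points the site to the wrong clock, and no earlier route is named for an outage during the study. The telephone option is stated only for the time after the tool is taken off-line at site completion.

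Second, Appendix 3 refers to a following section for the paper tool and to a separate document for contacts. That following section is not in the text available for this review. Its absence is not counted as an error, and it may contain an earlier route. This also stands, and it limits the conclusion. Even then, the trigger sentence would need to be aligned with it.

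Third, the 47-hour case requires a site that left a working system unused for 23 hours, and the documents give no outage frequency or duration. That is fair: 47 hours illustrates the rule and is not an expected delay.

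Fourth, the reach is limited. Primary and secondary endpoint events are waived from expedited reporting unless considered IMP-related (Sections 8.3.6 and 8.3.7). Section 8 separately requires immediate safety concerns to be raised with the sponsor at once, whatever the state of the electronic tool. Both points reduce the consequence but do not explain the 24-hour trigger.

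**Conclusion.** The concern holds in a limited form. The paper trigger is as long as the whole reporting window and is counted from the outage, so a site that waits for it reports late in the three-part situation shown above. In that situation, for outages longer than 24 hours, paper opens from just after 24 hours to about 47 hours in the cases worked. Outside it the limit can be met, so a general claim that the 24-hour limit is unachievable would be wrong.

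The conclusion rests on the clock starting at site awareness, on the site waiting for the stated trigger, and on the unseen paper-reporting section not already providing an earlier route. The AESI part rests on the cross-reference in Section 8.3.1. How often delay would occur cannot be judged from the documents. The point is operational: it does not touch the efficacy analysis, power or alpha. It is still worth correcting, because it concerns safety notification and the correction is small.

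**What to change.** Check the paper-reporting section that Appendix 3 refers to, then reconcile Appendix 3 with Section 8.3.1. Replace the sentence containing the more-than-24-hours trigger with:

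> *If the electronic system is unavailable, the site uses the paper SAE form in time to meet the 24-hour limit of Section 8.3.1, and enters the data electronically once the system is restored.*

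State that the same rule applies to AESIs. It would also help to say in Section 8.3.1 when the clock for an initial report starts, since the check above had to assume it.

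The cost is one replaced sentence and a short addition. The practical downside is occasional double entry after short outages. Appendix 3, read in context, already accepts double entry for longer outages by asking for electronic entry when the system returns.
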